6.0 Procedures Involved*

6.1 This study is a two arm prospective randomized trial to test the efficacy of public health messages about hookah tobacco use. All study procedures will be conducted by NORC staff in direct collaboration with the study team and investigators. Study participants will be anonymous to the study team and investigators, and all data collected as part of the study will be de-identified.

Participants will be recruited from the National Opinion Research Council's (NORC) AmeriSpeak consumer market research panel, screened for eligibility, and will complete a baseline assessment online. Then participants will be randomized in equal numbers to two arms: 1) hookah tobacco public education messaging or 2) control arm. On approximately a weekly basis for 4 weeks, participants will receive study communications and complete brief measures of message response online. For the hookah tobacco public education messaging arm, communications will consist of the study messages communicating about the health harms, addictiveness, social use, and flavorings in hookah tobacco. In response to each message, participants will complete measures of message response and hookah-related outcomes detailed below. Participants in the control condition will receive study communications with brief messages about health behaviors unrelated to tobacco (sun protection) and will complete the same measures. Study outcomes and hypothesized mediators will be assessed 2-, 4-, and 6-months after the message exposure period.

6.2 Trial participants will be 1,100 English speaking young adults ages 18 to 30 years old who have never used hookah tobacco but are deemed susceptible based on four screening questions or report hookah tobacco use at least once within the past month on valid measures. Trial participants will be recruited from the AmeriSpeak national consumer research panel maintained and operated by NORC. Although recruitment and data collection procedures will be conducted by NORC and all study participants will be anonymous to the investigators, our team will work collaboratively with NORC AmeriSpeak staff to oversee recruitment,

PROTOCOL TITLE: Randomized Trial Testing the Efficacy of Hookah Tobacco Public Education Messages among Young Adults

enrollment, data collection, and experimental procedures.

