AmeriSpeak panel members who are young adults ages 18 to 30 in the US will be sent a standard email invitation describing the study. Potential participants are identified by randomly selecting households within the panel with a young adult within the study age range, and targeting study invitations based on recent study participation, and other demographic characteristics as needed to ensure a representative sample. This email invitation will introduce study procedures and eligibility criteria, and direct interested panel members to the eligibility screener with items to confirm eligibility. Procedures will ensure potential participants are adults ages 18 and older through two steps: 1) targeting study invitations only to those panel members whose age is within this range; and 2) re-assessing age at eligibility screening and excluding those who provide inconsistent information (i.e., ages differ in self-reported screening compared with panel-based age derived from date of birth). Panel members who are confirmed to meet study eligibility criteria will proceed to the online baseline. AmeriSpeak panel members who do not meet study eligibility criteria will be redirected to a concluding thank-you screen. Similar procedures will be followed when participants are contacted for the brief message exposures and the 2-, 4-, and 6-month follow-up assessments. This approach is guided by similar previous tobacco research studies with young adults, including studies with prospective participation and retention rates of 70% and higher.⁴⁵⁻⁴⁶

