17.0 Data Management* and Confidentiality

17.1 We calculated statistical power to test our study hypotheses assuming a two tailed $\alpha = .05$ and baseline sample of 1100 participants, including 425 young adult hookah users and 675 susceptible non-users. We estimated the ability to detect effects of the messages on hookah initiation among susceptible non-users⁴⁴ and cessation among current users²¹ based on prior studies. Among susceptible non-users, we estimate 8% will initiate hookah use over the 6-month follow-up period based on our recent national study of US young adults.⁴⁴ With susceptible non-users at 6-month follow-up we will have 80% power to detect percent differences as small as 5.3%, or initiation of 8% in the control arm and 2.7% in the messaging arm. This equates to an odds ratio of 0.62 comparing hookah initiation between the messaging and control arms in a logistic regression analysis including covariates. Although evidence on hookah tobacco cessation rates is limited, 1 prior study found that young adult hookah users exposed to risk-based messages were nearly 2 times more likely than those in a control condition with no message exposure to report cessation at 6-month follow-up (62% vs. 33%, odds ratio 1.89).²¹ Conservatively assuming a much lower overall cessation rate of approximately 10% (i.e., comparable to those of behavioral smoking cessation interventions)⁵³ the sample of hookah users at the 6-month follow-up will have 80% power to detect absolute differences in cessation between study arms as small as 8% (10% control, 18% messaging). In a logistic regression analytic framework with covariates, this equates to an odds ratio of 1.55. For analyses of continuous outcome variables, our sample will provide 80% power to detect small mean differences ($d \leq 0.10$) between arms in the complete sample, and among susceptible non-users and current users separately. For testing mediating effects,

PROTOCOL TITLE: Randomized Trial Testing the Efficacy of Hookah Tobacco Public Education Messages among Young Adults

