simulation studies provide estimated power to detect mediation effects using bias-corrected bootstrap analyses.⁵⁴ The sample will provide 80% power to detect small- to medium- indirect (i.e., coefficients in the range of 0.20-0.30) effects. Similarly, for analyses of the interaction between study condition and two-level moderators we will have 80% power to detect moderator effects as small as Cohen's $f \leq 0.10$ in ANCOVA analyses (i.e., differences between susceptible non-users and hookah users) and odds ratios as small as 1.70 for interactions between non-hookah tobacco use and trial arm for binary initiation and cessation outcomes.

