We will test hypotheses about potential mediation of message effects through a series of steps drawing from traditional mediation frameworks for preliminary analyses⁵⁷ and applying more robust methods to formally test for mediation.⁵⁸ First, we will examine differences in means for mediating variables by trial arms and investigate whether each mediator at 1- and 3-month time points is correlated with the outcomes at 6-months using bivariate statistics and regression-based analysis accounting for any covariates as needed. Where these preliminary steps indicate potential mediation, we will formally test for mediation by estimating the indirect effects of candidate mediators at 1- and 3-months on study outcomes at 6-

PROTOCOL TITLE: Randomized Trial Testing the Efficacy of Hookah Tobacco Public Education Messages among Young Adults

months via the study arms using a bias-corrected bootstrapping method with 1,000 resamples to address non-normality of the product of the coefficients estimator.^{54, 58} This bootstrapping approach estimates an indirect (i.e., mediation) effect reflecting the product of the effect of trial arm on the mediator with the effect of the mediator on the outcome, and produces bias-corrected asymmetric 95% confidence intervals (CIs) that correct for non-normality of the distribution of indirect effects.⁵⁸ This method provides higher power and better control over the Type I error rate compared with traditional approaches for testing mediation.^{172,173} Asymmetric 95% CIs for indirect effects that do not include zero will indicate significant mediation effects.¹⁷² We will evaluate hypothesized moderators individually by introducing them one at a time and their corresponding interactions with trial arm into the logistic regression and ANCOVA models. Analyses assessing differential effects of messages among susceptible non-users and hookah users will primarily be ANCOVA based and examine mediators and outcomes measured commonly in these groups. Although the primary moderators of interest are those relating to hookah and other tobacco product use, we will also explore potential moderating effects of participant demographics including sex (male, female) and age (< 25, 25+) and other characteristics in analyses.

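### The formal mediation test for Hypothesis 2a runs only after preliminary steps with no stated criterion, and the 80% mediation power takes no account of them

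*Combined protocol and SAP*

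**What the plan says.** Hypothesis 2a (Section 2.2) names three mediators in advance: message engagement, message receptivity and perceived harms. Section 4.2 lists a wider set of secondary measures to be examined as mediators, including perceived risk, worry, emotional response and content recall.

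Section 17.1 sets out two stages. Each mediator is first compared between arms and then related to the 6-month outcomes, by bivariate statistics and by regression. Next: "Where these preliminary steps indicate potential mediation, we will formally test for mediation". The formal test is a bias-corrected bootstrap with 1,000 resamples, judged by whether the 95% CI excludes zero. No p-value or other criterion defines passing the first stage. A significant total effect is not among its steps.

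The reason given for the bootstrap is: "This method provides higher power and better control over the Type I error rate compared with traditional approaches for testing mediation". The power text says that "simulation studies provide estimated power to detect mediation effects using bias-corrected bootstrap analyses" and concludes: "The sample will provide 80% power to detect small- to medium- indirect (i.e., coefficients in the range of 0.20-0.30) effects". It does not mention the preliminary stage.

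**The concern.** The stated power belongs to a one-stage procedure, but the plan specifies two stages. A mediator must now pass the screen and then have an interval that excludes zero. A further condition can only lower the chance of a positive finding, so the 80% is an upper bound for what will actually be done.

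Two further consequences do not depend on power. Because the criterion is unstated, the choice of which mediators get a formal test is left to judgement after the data are seen. And if indirect effects appear only for mediators that passed, the reported values are selected for being large, while a mediator that failed has no indirect effect or interval. A reader could not then tell evidence against mediation from an imprecise estimate. For mediators named in a numbered hypothesis, nothing is gained by leaving this open.

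**Working it through.** **Inputs from the documents.** Two-sided alpha of .05 and a "baseline sample of 1100 participants, including 425 young adult hookah users and 675 susceptible non-users" (Section 17.1); equal allocation (Section 6.1); 1,000 resamples and a 95% interval (Section 17.1).

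**Assumptions.** The power text gives no 6-month n. Section 6.2 cites earlier studies with "prospective participation and retention rates of 70% and higher", so 70% is used: 0.70 × 1100 = 770; 0.70 × 675 = 472.5, taken as 472; 0.70 × 425 = 297.5, taken as 298. The scale of the 0.20-0.30 coefficients is not stated. Here *a* is the arm difference in the mediator in SD units, *b* is the slope of the outcome on the mediator, *a* = *b*, and there is no direct effect. Outcomes are continuous. The gate is taken as p<.05 for both the arm difference and the mediator-outcome correlation.

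**Step 1: reproduce the plan's figure.** With 2,000 simulated data sets per setting (Monte Carlo error about 1 point), ungated bootstrap power is 82.4% (n=770, 0.20), 80.8% (n=472, 0.25) and 78.0% (n=298, 0.30). The stated 80% for 0.20-0.30 is therefore met to within about 2 points on this reading. It is not met at 0.20 within the two subgroups (64.1% and 46.4%). With fully standardised paths it is exceeded: 90.6% at 0.20 with n=298.

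**Step 2: add the gate.**

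| n | a = b | Bootstrap alone | With p<.05 gate | Loss (points) |
|---|---|---|---|---|
| 770 | 0.20 | 82.4% | 79.0% | 3.3 |
| 472 | 0.25 | 80.8% | 77.7% | 3.0 |
| 298 | 0.30 | 78.0% | 73.2% | 4.8 |
| 472 | 0.20 | 64.1% | 58.0% | 6.2 |
| 298 | 0.25 | 64.3% | 57.4% | 6.8 |
| 298 | 0.20 | 46.4% | 38.1% | 8.3 |
| 472 | 0.30 | 91.9% | 90.2% | 1.7 |
| 770 | 0.30 | 98.7% | 98.4% | 0.3 |

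Losses were taken before rounding. With both standardised paths at 0.17 and n=298, power goes from 78.0% to 69.4% (loss 8.5). With a p<.10 gate the loss is 0 to 0.9 points throughout.

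**Step 3: check by hand.** In the tabulated settings the arm-difference screen does most of the work. Its power is Φ(*a*√n/2 − 1.96). For n=770 and *a*=0.20: 0.20 × 27.75/2 = 2.775; 2.775 − 1.96 = 0.815; Φ(0.815) = 79.2%, against 79.0% simulated for the gated procedure.

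**Step 4: compare with other tests (n=298, 0.25).** Gated bootstrap 57.4%; joint-significance test 57.5%; Sobel 45.6%; causal steps with a required total effect 5.4%.

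**Step 5: Type I error with one path zero.** In runs of 4,000 data sets, the ungated bootstrap rejected 5.8 to 6.7% and the gated procedure 3.2 to 4.6%. A second implementation (n=298, 4,000 data sets each) gave 7.6% against 5.3% (*a*=0, *b*=0.30) and 7.8% against 4.4% (*a*=0.50, *b*=0).

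**Step 6: selection of estimates.** Let z = *a*√n/2. Given passage of the arm screen, the expected ratio of estimated to true *a* is about [z + φ(1.96 − z)/Φ(z − 1.96)]/z.
- n=770, 0.20: z = 2.775, so (2.775 + 0.286/0.792)/2.775 = 1.13.
- n=472, 0.20: z = 2.173, so (2.173 + 0.390/0.584)/2.173 = 1.31.

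Simulation of the full product *ab* (10,000 data sets) gave the same 1.13 and 1.31. Without the gate the ratios were 1.00 and 0.99.

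**The case against.** The strongest reply is that the power gap is largely a difference in Type I error. When the ungated interval was run at alpha=.035 to bring its size nearer to nominal (it still rejected 5.5 to 6.5%), power at n=298 was 73.1% against 72.9% gated (*a*=*b*=0.30), and 69.5% against 67.5% (*a*=0.34, *b*=0.17). On that footing about 0 to 2 points remain. This stands: the gate does not throw away much information.

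The pilot effects in Section 3.2 are also much larger than 0.20-0.30: d=.89 for perceived harm and addictiveness in non-users and .74-.79 for perceived harm in users. With those values for *a*, the arm screen is nearly always passed and simulated losses were 1.5 to 4 points. This stands with a caveat: those were post-exposure measures in single experiments, and effects months later may be smaller.

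Screening has some merit too, given the many mediators in Section 4.2, several outcomes, more than one time point and no stated multiplicity adjustment. That supports keeping a screen for the exploratory mediators. It does not support an undefined one for the mediators in a numbered hypothesis.

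Finally, the screen yields arm differences and mediator-outcome associations, so a failed path would be visible. True, but neither is an indirect effect with an interval, which is what Hypothesis 2a concerns.

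A reader might infer that the gate cancels the advantage claimed for the bootstrap. The evidence does not support this. Only the gain over a joint-significance test is lost, and only at about p<.05. The gated procedure still beats Sobel and causal steps, and its Type I error is lower.

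**Conclusion.** The point holds in a limited form. It follows from the text alone that the gate exists, has no criterion, applies to pre-named mediators and is absent from the power statement. The size does not follow from the text. With an assumed p<.05 gate the loss is roughly 2 to 8 points in most plausible settings, 3 to 5 where the plan's own 80% is reproduced, and close to zero where power is very high. At p<.10 it is under 1 point. A reader might take one figure from this range as a fixed cost of the plan; without a threshold in Section 17.1, no single figure is justified.

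The better reasons to change are the undefined, data-dependent choice and the upward selection of reported effects (about 13 to 31% in the settings checked where ungated power is about 64 to 82%). All figures rest on 70% retention, the assumed effect scale, continuous outcomes and no direct effect. The binary initiation and cessation outcomes would need their own simulation. The primary arm comparison is not affected.

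**What to change.** In Section 17.1, remove the condition for Hypothesis 2a. State that the indirect effect and its bootstrap 95% CI will be estimated and reported for message engagement, message receptivity and perceived harms, whatever the preliminary results. Tie each to a named measure and time point; Section 4.2 does not list engagement by that word. Keep the arm comparisons and mediator-outcome associations as description. A screen may stay for the other, exploratory mediators in Section 4.2, with its threshold and deciding statistic written down.

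If the sponsor prefers to keep the gate for Hypothesis 2a, define it and recompute the mediation power for the two-stage procedure.

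The cost is a few sentences and a few bootstrap runs. Non-significant indirect effects will also be reported, and the false-positive rate with one path zero rises to about 6 to 8%, against about 3 to 5% under a p<.05 gate. The plan should acknowledge this, and should drop or qualify its statement about better Type I error control.

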2.0 Objectives*

2.1 The purpose of this study is to examine the efficacy of hookah tobacco public health education messages among young adults between the ages 18 to 30, including young adults who are susceptible non-users of hookah tobacco and current users.

2.2 Hypothesis 1: Messages will decrease hookah initiation among susceptible non-users and increase cessation among hookah users.

Hypothesis 2a: Message effects will be mediated by greater message engagement, message receptivity, and perceived harms of hookah tobacco.

Hypothesis 2b: Message effects will be greater among susceptible non-users versus hookah users and among those who do not use other tobacco products versus those who do.

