The online baseline assessment includes valid measures of hookah and other tobacco use behavior, hookah beliefs, perceptions, and other constructs from our conceptual framework. After completing a baseline, participants will be randomly assigned in approximately equal numbers to one of two arms: 1) hookah tobacco education messaging; 2) control arm. Randomization will be balanced by hookah use status (susceptible non-user, current user) to ensure sufficient numbers of these characteristics across study arms. Participants in the hookah education messaging arm will then receive 4 study communications delivered approximately weekly during the exposure period. These communications will consist of: 1) the study hookah education messages; and 2) brief post-message (approximately 5 minutes) measures of hookah use behaviors, beliefs and perceptions, and message responses. Procedures for participants randomized to the control arm will be similar, however communications will consist of non-tobacco messages communicating about sun protection that we have developed on our previous work and pilot tested against tobacco-related messaging to ensure they are an adequate contact-matched control. Messages will have a similar layout and structure (e.g., amount of text) to the hookah public education messages and will be presented in a consistent order for all participants. We chose this contact-matched control arm to ensure groups are treated equivalently with only message content varying between arms.

PROTOCOL TITLE: Randomized Trial Testing the Efficacy of Hookah Tobacco Public Education Messages among Young Adults

All participants will complete follow-up assessments online 2-, 4-, and 6-months after the message exposure period. We chose these time points based on our team's prior work on young adult tobacco use behavior and messaging,^{44, 45} other research on hookah tobacco messaging,²¹ recommendations for follow-up in tobacco intervention research,^{47, 48} and because this follow-up frequency and duration will capture short term message effects and changes in hookah use, susceptibility, and mediating processes.^{12, 14, 21, 47, 49-52} As with the baseline, follow-ups will be securely administered online. Measures are attached in Section 14. At the conclusion of the final follow-up, all participants will be debriefed on the study goals and the potential risk of hookah and other forms of tobacco use.

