The primary outcomes and analytic approach will compare differences in 6-month outcomes across the control and messaging arms. We will initially assess differences in past 30-day hookah use behavior using longitudinal mixed effects logistic regression in the entire sample. The model will include past 30-day hookah use at 6 months as the dependent variable, trial arm, and baseline covariates for susceptible non-user/current user and any others identified in the steps outlined above.⁵⁵ We will then use a similar modeling strategy to assess differences by trial arm in hookah use initiation among participants who were susceptible non-users at baseline, and cessation among baseline users. These analyses will model dependent variables reflecting change in hookah use status from baseline to the 6-month follow-up separately for these two groups, a term for trial arm, and any covariates as identified above. Among susceptible non-users at baseline, we will similarly analyze changes in susceptibility status relative to trial arms as a secondary outcome. In both susceptible non-users and hookah users, will also conduct analyses to assess message effects on continuous outcome measures at 6 months, curiosity to use hookah tobacco and motivation to quit, respectively. We will use repeated measures ANCOVA to compare means of the continuous outcomes by trial arm at 6 months and Tukey's adjustment method for the pair-wise comparisons. In exploratory analyses, we will repeat these types of mixed logistic and ANCOVA analyses for outcomes measured at the 1- and 3-month time points. We will assess any potential message order effects separately in the education messaging arm by examining message effects by the 4x4 Balanced Latin Square orders. If any message order effects are detected or trends are observed we will include order as a covariate in analyses.⁵⁶ Exploratory analyses will also examine if responses to weekly assessments differ by message themes using approaches similar to those above.

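### The mediation models for perceived harm and related beliefs do not pre-specify the baseline value of the mediator, so a belief-behaviour correlation that predates randomisation could be declared a message mechanism.

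*Combined protocol and SAP*

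**What the plan says.** Hypothesis 2a (section 2.2) reads: "Message effects will be mediated by greater message engagement, message receptivity, and perceived harms of hookah tobacco". Section 4.2 adds perceived addictiveness, perceived risk and worry to the variables to be examined as mediators.

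Section 17.1 proceeds in two steps.

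- **Screening.** Mediator means are compared by arm, and each mediator is related to the 6-month outcome by bivariate statistics and "regression-based analysis accounting for any covariates as needed".
- **Formal test.** "Where these preliminary steps indicate potential mediation, we will formally test for mediation", using a bias-corrected bootstrap with 1,000 resamples. The estimand is "the product of the effect of trial arm on the mediator with the effect of the mediator on the outcome".

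No covariate is named for the formal test. The main outcome models in the same section refer to "any others identified in the steps outlined above", but the available text shows no such steps.

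On data, section 6.2 states: "The online baseline assessment includes valid measures of hookah and other tobacco use behavior, hookah beliefs, perceptions". Randomisation follows that assessment. Message reactions are collected only after exposure, among the weekly "measures of hookah use behaviors, beliefs and perceptions, and message responses".

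**The concern.** The arm-to-mediator path is a randomised comparison. The mediator-to-outcome path is an observational regression within the trial. Someone who already thought hookah harmful at enrolment will tend to score higher on perceived harm later and to use less later, whatever the messages do. Unless the model holds that starting point fixed, the second path absorbs it. Once the messages shift the mediator, the product of the two paths is no longer centred on zero.

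The screening step does not guard against this. It passes a mediator when the arms differ on it and it correlates with the outcome, and those are the two conditions that generate the false finding. The bootstrap deals with the non-normality of a product, not with confounding.

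At stake is the mechanism reported for a pre-specified hypothesis. An interval excluding zero could mean only that the messages moved beliefs and that beliefs and behaviour were already related.

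**Working it through.** **Inputs from the documents.** 675 susceptible non-users and 425 users; 1:1 allocation; two-sided 0.05; 8% initiation and 10% cessation (section 17.1). Pilot effects on perceived harm and addictiveness were d = 0.89 in never-users and 0.47-0.80 in users (section 3.2).

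**Assumptions.** Retention of 70%, which section 6.2 cites only for earlier studies, gives 0.7 x 675 = 472 and 0.7 x 425 = 298. The documents give no retest correlation (r) or baseline belief-outcome correlation (rho). I take r = 0.5-0.6 and rho = 0.2-0.3, with 0.4 and 0.1 as a weak case. The message effect on the mediator is d = 0.3-0.5, lower than most of the pilot values.

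**1. The plan's own mediation figure.** Section 17.1 states 80% power for coefficients of 0.20-0.30. Approximate power as P(path a significant) x P(path b significant), with a in SD units, se(a) = 2/sqrt(N) and se(b) = 1/sqrt(N). For a = b = 0.20 and N = 770 (70% of 1,100):
- z_a = 0.20 x sqrt(770)/2 = 2.77, power 0.792
- z_b = 0.20 x sqrt(770) = 5.55, power about 1.00
- product 79%

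The stated figure is attainable, although the plan gives neither the metric nor the analysed N. It does not address bias.

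**2. The bias.** Let B be the baseline belief, M = rB + d x arm + error, and Y = -rho x B + error, with unit variance within arm. M has no effect on Y. Regressing Y on arm and M gives b = cov(M,Y | arm)/var(M | arm) = -r x rho, so the expected indirect effect is -d x r x rho instead of 0.
- d = 0.45, r = 0.5, rho = 0.2: -0.45 x 0.10 = -0.045 (simulated mean -0.0454)
- d = 0.45, r = 0.7, rho = 0.3: -0.45 x 0.21 = -0.0945 (simulated mean -0.096)

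With B in both regressions, the simulated means lie within about 0.006 of zero.

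**3. False-positive rate, continuous outcome, n = 472.** Here se(a) = 2/sqrt(472) = 0.092 and se(b) = sqrt((1 - b^2)/472).

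| r, rho | size of b | z_b | P(b sig.) | joint, d = 0.3 | joint, d = 0.5 |
|---|---|---|---|---|---|
| 0.5, 0.2 | 0.10 | 2.18 | 0.59 | 0.53 | 0.59 |
| 0.6, 0.3 | 0.18 | 3.98 | 0.98 | 0.88 | 0.98 |
| 0.4, 0.1 | 0.04 | 0.87 | 0.14 | 0.13 | 0.14 |

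P(a significant) is 0.90 at d = 0.3 (z = 3.26) and about 1.00 at d = 0.5 (z = 5.43). Simulating the planned bias-corrected bootstrap in the main settings gives 61-99%, against 3-7% with B. The weak case gives 8-18% over the sample sizes examined, against 3-6%. A wider bootstrap grid (r up to 0.7, d = 0.20-0.75, n = 298 and 472, 200 trials per cell) gives about 20-100% without B and 4-12% with it; Monte Carlo error is about 2 to 4 points.

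**4. Binary outcomes.** Same assumptions, with a thresholded outcome, a logistic second path and joint significance:
- 8% initiation, n = 472: about 20-58% without B
- 10% cessation, n = 298: about 11-44% without B
- weak correlations: near nominal, up to about 15%

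Specifying the link instead as an odds ratio of 0.7-0.5 per SD of baseline belief gives 18-63% and 11-51% without B, against 3-8% and 4-5% with it.

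**5. Limits of the effect.** With no arm effect on the mediator (d = 0), the unadjusted rate is 2-13% and the mean indirect effect is about zero. With no baseline belief-outcome link (rho = 0, d = 0.75), it is 4-6%. Both conditions must be present.

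**The case against.** Several points on the other side stand.

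- **Scope.** A reader might infer that all Hypothesis 2a models ignore a baseline value that was collected. They do not. Engagement and receptivity are reactions to study messages, so no pre-randomisation value can exist. The point covers perceived harm and the related belief mediators, where these were measured at baseline.
- **Open, not excluded.** A reader might infer that the plan rules out the baseline mediator. It does not: the screening step allows covariates as required, and the rates above show the reading in which none is used. But the choice is left until the data are in hand, and it can decide the result.
- **Outcome type.** The 55-99% range applies to continuous outcomes such as curiosity and motivation. It should not be carried over to initiation or cessation, where the inflation is smaller.
- **Partial protection.** Section 17.1 plans repeated-measures ANCOVA for curiosity and motivation. It does not say that the baseline outcome enters the mediation model. If it did, with assumed stability 0.6, joint-significance rates at n = 472 would fall from 54-97% to 18-52%, and to 6-8% under weak correlations. That helps but does not restore 5% in the main settings.
- **The adjusted rates are favourable by construction.** In the simulations the baseline belief is the only confounder and is measured without error. Other tobacco use or peer influence could still confound the second path in the real trial.

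**Conclusion.** The concern holds for perceived harm, perceived addictiveness, risk and worry, as a failure to pre-specify. The formal mediation model does not fix the baseline mediator, the trial collects hookah beliefs and perceptions before randomisation, and the pilot effects make movement of the mediator likely. Under the main assumptions and with no true mediator effect, false mediation would be declared in about 55-99% of trials for continuous outcomes, 20-60% for initiation and 11-44% for cessation, against about 3-7% with the baseline mediator. Weak correlations give about 5-18%. The direction follows from algebra; the size rests on correlations that the documents do not report.

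Two stronger conclusions are not supported. The documents do not show that Hypothesis 2a would be confirmed regardless of the truth, only that its belief components could be. Nor is the Hypothesis 1 efficacy comparison affected, because it does not use the second path.

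**What to change.** In the mediation paragraph of section 17.1, state that both regressions of each belief-mediator model include:

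1. the baseline value of that mediator;
2. the baseline value of the outcome where it varies: curiosity in susceptible non-users, and motivation and use frequency in current users only (baseline use is constant in people who have never used hookah);
3. hookah-use status when the two groups are pooled.

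Describe the resulting indirect effect as conditional on these covariates and still open to other mediator-outcome confounding. For engagement and receptivity, say that no baseline value exists, that this adjustment does not protect them, and that their indirect effects will be reported with that caveat.

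The cost is a few sentences in the analysis plan, settled before outcome data are examined. No new data are needed where the belief was measured at baseline.
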